MULTI-SITE RESEARCH: N/A

STUDY TIMELINES:

Subject's participation in the study will last 1 year

Approximately 5 TKA surgeries are performed each week at the Feinberg Pavilion. If we are able to enroll 5 subjects per month it should take about 24 months to complete.

STUDY ENDPOINTS:

Primary Outcome:

-Post-operative opioid consumption during the hospital stay.

Secondary Outcome:

-Pain scores (Visual Analog Scale pain score; 0 = no pain, 10 = excruciating pain) in the knee at rest and during activity recorded every 6 hours up to discharge.

- Overall global pain score (VAS pain scores; 0 = no pain, 10 = excruciating pain) recorded every 6 hours up to discharge.
- Overall pain burden for the first 36 hours.
- Opioid related side effects
- Time to physical therapy milestones (active straight leg raise, time until patient first gets out of bed, ambulation about the hospital room with or without assistance, ambulating 100 feet and ability to climb stairs)
- Length of hospitalization
- Readmission to the hospital or emergency room visit for evaluation during study period.

PROCEDURES INVOLVED:

All ASA 1-3, 40-85 year old patients who are scheduled for total knee reconstruction surgery and are scheduled to receive a nerve block as part of their postoperative analgesic care will be approached to participate in this study. Patients will be introduced to the study in the Lavin Pavilion 12th floor pre-operative clinic by one of the study team members. On the day of surgery in the Feinberg pavilion 5th Floor. The subject will be approached by one of the study team members to answer any questions they have regarding the study. If they had not signed the consent document in the pre-operative clinic they will be asked again if they had reviewed the consent document and whether they would like to participate. Patient participation will last for 12 months.

Sealed opaque envelopes will be pre-randomized into two study medication groups using a computerized random number generator.

The study medication and protocol will consist of Group 1 (Active) – ultrasound-guided adductor canal blockade with 10 ml of 0.25% bupivacaine and ultrasound-guided genicular nerve blocks with 6 ml of 0.5% bupivacaine, and Group 2 (Control) – ultrasound-guided adductor canal block with 10 ml of 0.25% bupivacaine and ultrasound-guided genicular nerve blocks with 6 ml of normal saline. The surgeon will be blinded to the subjects study arm assignment.

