A study team member will follow up patients by telephone (if discharged prior to) at 48 hours, 72 hours and at 3 weeks and will ask questions pertaining to the patient's pain, narcotic side effects, and satisfaction with pain control. Patients are scheduled to have a follow-up visit with their orthopedic surgeon at approximately 3 weeks and 1 year following surgery. The range of motion, current pain medication use, pain scores and untoward events will be re-recorded during each surgical follow-up visit. Patient's medical record will be reviewed to verify or obtain correct opioid consumption and physical/occupational therapy participation during hospital stay.

DATA AND SPECIMEN BANKING: N/A

DATA AND SPECIMEN MANAGEMENT:

Study members will have an active Collaborative Institutional Training Initiative (CITI) training certification. Their names and roles will be added to the IRB application.

Each study subject will be assigned a study code number. The code will be used to link study data to patient identification (name) in a separate database that only the investigator has access.

Strict measures will be in place to ensure that no loss of confidentiality occurs. Only study team members will have access to the data. The principal investigator will be responsible for handling and management of the data.

Subject data will be stored on password protected secure computer at Northwestern University 10th floor Arkes (Department of Anesthesiology administrative office). Data access will be password protected and only available to study team members. Access will be controlled by the Principal Investigator. Local data will be stored on Northwestern University, NM servers which are password protected and backed up nightly. Information regarding the perioperative course will be included in the data collection. Data will also be validated by the PI prior to data analysis.

Data will be stored on NM Servers and Department of Anesthesiology computers which are password protected. Paper data will be stored in Arkes Pavilion 10th floor Department of Anesthesiology office research closet which is accessible by key card entry and then key for the closet. Each study subject will be assigned a study code number. The code will be used to link study data to patient identification (name) in a separate database.

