The data both electronic and paper will be stored for five (5) years after manuscript preparation. Data both electronic and paper will be destroyed using departmental standards and approved vendors.

PROVISIONS TO MONITOR THE DATA TO ENSURE THE SAFETY OF PARTICIPANTS:

At the start of the study, a Data and Safety Monitoring Board (DSMB) will be appointed and will consist of the PI, a regional anesthesiologist, a statistician ([name]) all with expertise in the area of regional anesthesia complications after blocks for orthopedic surgery. The DSMB members must attest to not having any conflicts of interest with the study. A study team member (TBD) will participate in the DSMB meetings as non-voting member. The DSMB will be charged with oversight of the study's safety and integrity and assessing the risk versus benefits of continuing the study if such questions arise. The DSMB will meet annually in person or by conference call or more often, if necessary, based on the progression of the study. The DSMB will continue to meet until the completion of the study.

The DSMB will review patient recruitment and patient follow-up, compliance with the protocol including protocol violations, timeliness and completeness of data entry, compliance with patient confidentiality and HIPPA regulations, and communications of adverse events to the IRB. The DSMB members should immediately review the data in order to make any requests for additional information or analysis in a time frame that can allow for such requests to be completed before the scheduled DSMB meeting. Members of the DSMB must maintain confidentiality of the study data until otherwise instructed. An interim analysis of the data looking at safety will be conducted by the DSMB when results from the first 50 subjects are available.

WITHDRAWAL OF PARTICIPANTS:

If the subject decides to discontinue their participation in the study, no further exams will be completed. The existent data sheet will be preserved and the removal of a partially completed subject from the data set will be noted in the study manuscript. A research team member will contact the PI by secured-email to inform him about the event that led to early study termination.

RISKS TO PARTICIPANTS:

ACB is a widely practiced technique performed to provide postoperative analgesia for patients undergoing total knee arthroscopy. The major risk of genicular nerve block is infection, which is exceedingly rare given the use of aseptic technique.

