- The study will be conducted in one of pre and post-operative rooms in the PACU on the 5th floor Feinberg Pavilion.
- Participants will have the immediate availability of the supervising anesthesiologist and attending anesthesiologist of record.
- Participating anesthesiologists and operating room staff and study team members will be briefed on the study prior to the subjects block.

PRIOR APPROVALS:

Department of Anesthesiology Research Committee

RECRUITMENT METHODS:

Subjects will be approached and recruited by a member of the anesthesia research team during the pre-operative clinic visit on the 17th floor Lavin Pavilion of Northwestern Memorial Hospital. Study team members will use Powerchart and Epic from NW to screen potential participants

Describe materials that will be used to recruit subjects. N/A

NUMBER OF LOCAL PARTICIPANTS:

On the basis of the literature ⁶ we assumed that patients in Group B (Control group) will have an average opioid consumption at 36 hours following surgery of 48 mg IV morphine equivalents (morEq) while patients who receive genicular nerve blocks would experience a decrease of 20% in opioid consumption to an average of 39 mg IV morEq. Standard deviation was estimated to be 15. The effect size is 0.60. Comparison of means of two independent groups (Wilcoxon-Mann-Whitney Test) demonstrated a required total sample size of 94, 47 participants in each group. 80% power, 0.05 alpha level. Six patients will be added to account for lost to follow up or cancelled surgical cases.

Pain burden defined as the area under the numeric rating score for pain for the first 36 hours will be calculated using the trapezoidal method. Time to report first pain and overall patient satisfaction between groups will be compared using the Kruskal-Wallis H test.

CONFIDENTIALITY:

Data is collected on paper by study team members and then entered onto the Department of Anesthesiology password controlled computers located on the 10th floor Arkes Pavilion. Data are stored in a department (NM) server which is also password protected and backed up nightly. Each study subject will be assigned a study code number. The code will be used to link study data to patient identification (name) in a separate database.

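### The withdrawal rule takes partially completed subjects out of the data set, so a patient who withdraws after discharge can be excluded despite complete primary data

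*Protocol*

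**What the plan says.** The only rule on who leaves the data set is in the protocol section Withdrawal of Participants. Its trigger is "If the subject decides to discontinue their participation in the study", with no time limit. Further examinations then stop, the data sheet is kept, and "the removal of a partially completed subject from the data set will be noted in the study manuscript". The section does not define a partially completed subject and does not tie the term to the primary outcome.

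Three other parts of the protocol bear on this rule:

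- **Study Endpoints** gives the primary outcome as "Post-operative opioid consumption during the hospital stay". The sample size section uses the 36-hour total.
- **Procedures Involved** states that "Patient participation will last for 12 months". After discharge there are telephone contacts at 48 hours, 72 hours and 3 weeks, and surgeon visits at about 3 weeks and 1 year. The same section says that the "medical record will be reviewed to verify or obtain correct opioid consumption" for the hospital stay.
- **Number of Local Participants** sets 94 patients and adds an allowance: "Six patients will be added to account for lost to follow up or cancelled surgical cases".

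The SAP covers pain burden, time to first pain and satisfaction. It names no analysis set, does not say that patients are analysed as assigned, and has no rule for missing data.

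**The concern.** The primary outcome is known when the patient leaves hospital, but the patient stays under study for about a year. For all that time a patient who withdraws is, in the ordinary sense, only partially completed, and the rule takes removal for granted. Primary data that already exist can be discarded because of a later decision that has no bearing on whether they are complete.

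That is an exclusion after randomisation. Follow-up asks about pain, narcotic side effects and satisfaction, and the section Risks to Participants accepts that such questions may make subjects uncomfortable. The trial's hypothesis is that the block lowers opioid use and so reduces side effects and improves satisfaction. If the decision to withdraw depends on any of these, the patients who remain are no longer a randomised comparison. A lesser cost is that these removals use up spare patients already meant to cover loss to follow-up and cancelled surgery.

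**Working it through.** **1. Timing.** The text side by side:

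| Item | When it ends | Protocol section |
|---|---|---|
| Primary outcome as listed | Hospital discharge | Study Endpoints |
| Primary outcome as sized | 36 hours | Number of Local Participants |
| Last telephone contact | 3 weeks | Procedures Involved |
| Last visit | About 1 year | Procedures Involved |
| Withdrawal rule | No end point given | Withdrawal of Participants |

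On either definition the primary outcome normally closes well before the 3-week and 1-year contacts. Between discharge and 1 year, a patient can have a complete primary outcome and still fall within the withdrawal rule.

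**2. Is the patient restored elsewhere?** No. Neither document has an intention-to-treat statement, a definition of the analysis population or a missing-data rule. Keeping the data sheet is stated in the same sentence as removal from the data set, so keeping the one does not amount to inclusion in the other.

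**3. The protocol's sample size.** Inputs from Number of Local Participants: means 48 and 39 mg IV morphine equivalents, SD 15, Wilcoxon-Mann-Whitney test, alpha 0.05, power 80%, 47 per group. The protocol does not say whether alpha is two-sided; two-sided is assumed.

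- Effect size: d = (48 − 39)/15 = 0.60, as stated.
- Effective n per group: m = (N/2) × 3/π, where 3/π is the efficiency of the rank test relative to the t-test under normality.
- Noncentrality: d × √(m/2), with 2m − 2 degrees of freedom.
- At N = 94: m = 47 × 0.955 = 44.88; noncentrality = 0.60 × √22.44 = 2.842; power = 80.3%.

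This reproduces the planned 94 patients at 80%. Adding six gives 100.

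**4. Power as patients are lost from the analysis** (same formula, equal arms):

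| Lost of 100 | Analysed | Power | Status of the loss |
|---|---|---|---|
| 0 | 100 | 82.7% | All kept |
| 6 | 94 | 80.3% | Planned allowance |
| 7 | 93 | 79.8% | One beyond the allowance |
| 10 | 90 | 78.5% | Assumed |
| 20 | 80 | 73.5% | Assumed |

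The documents give no withdrawal rate, so the last two rows are illustrations. If withdrawals after discharge are kept, they cost the primary analysis nothing.

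**The case against.** The strongest reply is that the text is unclear rather than wrong. It never orders the removal of everyone who discontinues; it keeps the sheet and promises to report removals. A partially completed subject could mean one whose in-hospital data are incomplete. It is true that the exclusion is permitted and not certain. But the term is undefined, the trigger has no time limit, and no other text limits it. The choice would then be made after the data are in, which a pre-specified plan should prevent.

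Second, the scenario may be rare. The rule concerns a patient who actively decides to stop. Missing a call is not the same thing, and the 3-week and 1-year visits are with the patient's own surgeon. This stands: the number affected may be small, and the documents do not say whether patients merely lost to follow-up are also removed.

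Third, bias is not demonstrated. The control arm receives saline injections at the same sites and postoperative follow-up is blinded. That lessens the risk that knowledge of the arm drives withdrawal. It does not remove the route through pain, side effects or satisfaction, because those are the effects under test. Noting the removals in the manuscript discloses the exclusion without reversing it.

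Fourth, the power argument is weak, and the allowance of six does not name withdrawals. Both points stand. Power is not the main reason to change the rule.

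**Conclusion.** The concern holds. As written, the rule allows a randomised patient with a complete primary outcome to be excluded from the primary analysis because of a withdrawal up to a year later, and nothing in either document prevents it. It should be fixed.

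No size or direction of bias is claimed, since the documents give neither withdrawal rates nor reasons. The loss of power is minor unless losses clearly exceed six. The power figures assume a two-sided test, equal arms, normally distributed data for the 3/π factor, and the protocol's own effect size of 0.60. The conclusion about exclusion depends on none of these; it rests on the wording and on the gap between discharge and 12 months.

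**What to change.** Replace the removal rule in the protocol, and put the same text in the SAP. Suggested wording:

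> Data collected up to withdrawal are retained and analysed unless the subject withdraws permission to use them. The primary analysis includes all randomised patients who had surgery, in the arm assigned. Withdrawal from, or loss to, later follow-up does not remove a patient from analyses of outcomes already observed. If a patient withdraws during the hospital stay, opioid consumption for the full primary window is obtained from the medical record where permission allows; otherwise it is treated as missing, not as a truncated total.

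The last sentence matters because a total cut short by withdrawal would otherwise count as low opioid use. Delete the term *partially completed* or define it, and report withdrawals by arm with timing and reason.

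The cost is a wording change in two documents and no extra patients. Review of the medical record for in-hospital opioid use is already planned. Using the record after withdrawal depends on the permission given in the consent form, which was not available for this review and should be checked.

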Appendix A

DATA COLLECTION FORM Ultrasound-guided genicular nerve block

Investigator: [name].

Subject: ____ • **Date of procedure:** ____ / ____ / ____ TKA

description: _____

Surgical Procedure: L R

Baseline (24hr) pain score: _____ Sex:

M F Weight: ____ lbs/kg • Height: ____ in Age: ____

Subject Demographics: Caucasian: ____ African American: ____ Asian: ____ Hispanic: ____

Middle Eastern: ____ Other: _____

Time to complete block (needle in–needle out): _____

Time of block placement: ____ Sensory Assessment at 30 minutes: Yes No

Pain Score (VAS 0-10) after the performance of the block: _____

Immediate Complications: None Yes If yes, explain:

Delayed Complications: None Yes If yes, explain:

Follow-up: Time to 1st pain: _____ **Location:** _____

	6hr	12hr	18hr	24hr	30hr	36hr	42hr	48hr
Time:								
NRS (0-10)								
At rest								
During Activity								
Pain medication:								
Norco ____ mg								
Oxycodone								
Dilaudid								
Side effects (0-3)								
1=mild, 2=mod, 3=severe								
Nausea								
Vomit								
Dizzy								
Patient Satisfaction (0-10) Pain Control								

Anterior ____ **Posterior** ____ **Other** _____

Physical Therapy Milestones	Time
Active straight leg raise	
Time until patient first gets out of bed	
Ambulation about the hospital room with or without assistance	
Ambulating 100 feet	
Ability to climb stairs	

Time of Discharge: _____ Date: ____ / ____ / ____ Length of hospitalization: _____

	72hr	3wks
Time:		
NRS (0-10) At rest During Activity		
Pain medication: Norco ____ mg Oxycodone Dilaudid Tramadol		
Side effects (0-3) 1=mild, 2=mod, 3=severe Nausea Vomit Dizzy		
Patient Satisfaction (0-10) Pain Control		

Follow up:

Pain Scores (0-10)

At Rest: @ 3wk _____ and @ 1year _____

During Activity: @ 3wk _____ and @ 1year _____

Block Satisfaction @ 3wk (0-10):

VS S Not Sat nor US US VUS

Range of motion: @ 3wk _____ and @ 1year _____.

Readmission to the hospital or emergency room visit:

Yes No

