STU#:00204116

PROTOCOL TITLE: A Comparison of Analgesic Efficacy of Ultrasound-Guided Genicular Nerve Block versus Saline Injection for Total Knee Replacement: a Prospective, Randomized Controlled Trial

PRINCIPAL INVESTIGATOR:

[name]

Institution: Northwestern University, Feinberg School of Medicine

Department: Anesthesiology

Address: [name]

Email Address: [contact]

[contact]

[contact]

VERSION NUMBER: 1.0

VERSION DATE: 09/12/2017

OBJECTIVES:

Research Questions:

Do ultrasound-guided genicular nerve blocks with 0.5% bupivacaine provide improved knee analgesia for patients recovering from total knee replacement surgery compared to saline injection?

Hypotheses:

We hypothesize that the combination of ultrasound-guided adductor canal block (ACB) and genicular nerve block will achieve lower opioid consumption and therefore lead to decreased systemic side effects and improved overall satisfaction compared to ultrasound-guided saline injection for patients undergoing minimally invasive elective total knee arthroplasty (TKA).

BACKGROUND:

Total knee arthroplasty is associated with intense early postoperative pain. A sizeable proportion (25–40%) of patients experience severe pain postoperatively despite a comprehensive multimodal analgesic regimen.¹ Enhanced recovery protocols that emphasize early mobilization and hospital discharge remain varied among hospitals. Regional anesthetic techniques have evolved to preserve motor function in an effort to promote early ambulation and hospital discharge, while optimizing sensory blockade for adequate analgesia. The (ACB) of the saphenous nerve has demonstrated reduced opioid consumption and preservation of quadriceps muscle strength when compared to placebo and to femoral nerve blockade² however, several studies have shown that despite ACB, many patients may still have at least moderate, movement-related pain. This may be partly because the ACB does not provide analgesia to the posterior aspect of the knee, in which pain is commonly moderate to severe after surgery.

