Subject's involvement may make them feel emotionally uncomfortable because study team members will ask them questions regarding their pain and satisfaction throughout the study period.

The risks of the study medication include unintentional intravascular injection of the local anesthetic solution. This may cause cardiovascular effects such as hypotension, bradycardia, ventricular arrhythmias or cardiac arrest. Allergic response which can be mild or as severe as anaphylaxis. Rare risks include restlessness, anxiety, dizziness or tremors.

There is the risk of loss of confidentiality even though there are strict measures in place to prevent occurrence.

POTENTIAL BENEFITS TO PARTICIPANTS:

The potential benefit of participating in the study is that patients receiving the both the ACB and genicular nerve block may take less pain medication resulting in fewer side effects and achieve physical therapy milestones sooner than those who do not receive an genicular nerve block.

VULNERABLE POPULATIONS: N/A

COMMUNITY-BASED PARTICIPATORY RESEARCH: N/A

SHARING OF RESULTS WITH PARTICIPANTS: N/A

SETTING:

Study participants will be identified and recruited from the Anesthesiology pre-operative clinic on the 17 Floor of Lavin Pavilion at Northwestern Memorial Hospital. The research will be performed in the pre and post-operative area at Feinberg Pavilion 5th Floor. Post-surgery evaluations will occur on the orthopedics floors on the Feinberg Pavilion. The 3 week and 1 year follow up will occur in the orthopedic surgeon's office within Northwestern Medicine.

RESOURCES AVAILABLE:

The Section of Regional Anesthesiology actively provides care to admitted patients at Feinberg Pavilion. As a Regional Anesthesiologist and member of the Anesthesiology Service I regularly supervise and provide care to patients on this unit. We have a dedicated group of study team members that assist with daily recruitment and follow-up of patients in clinical anesthesiology trials. Study team members all have CITI training.

The primary investigator has expertise using the ultra-sonographic probe for needle guidance for nerve blocks. The study team members will set up the ultrasound machine for each study participant.

- The ability to recruit the number of study participants should be fairly easy given the number of TKA performed yearly.
- The investigator will be present for all scheduled study related nerve blocks.

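### The side-effect hypothesis can be only partly tested: opioid side effects are undefined, scored on three symptoms only, and have no planned analysis

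*Protocol*

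**What the plan says.** The Hypotheses paragraph of the protocol states that the combined blocks "will achieve lower opioid consumption and therefore lead to decreased systemic side effects and improved overall satisfaction". Background repeats the claim, and Potential Benefits to Participants offers fewer side effects as a reason to take part. Study Endpoints lists "Opioid related side effects" among the secondary outcomes, without components, score or time point.

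The form in Appendix A supplies the only structured content: "Side effects (0-3) 1=mild, 2=mod, 3=severe Nausea Vomit Dizzy". The same three items appear on the 6–48 hour grid and on the grid for 72 hours and 3 weeks.

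Risks to Participants says of the study drug: "Rare risks include restlessness, anxiety, dizziness or tremors". Under Procedures Involved, the active arm receives "ultrasound-guided adductor canal blockade with 10 ml of 0.25% bupivacaine and ultrasound-guided genicular nerve blocks with 6 ml of 0.5% bupivacaine" and the control arm "ultrasound-guided adductor canal block with 10 ml of 0.25% bupivacaine and ultrasound-guided genicular nerve blocks with 6 ml of normal saline".

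The SAP covers pain burden, time to first pain and satisfaction. It does not mention side effects. Nor does the analysis text in the protocol under Number of Local Participants.

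**The concern.** The hypothesis concerns systemic side effects in general, while the instrument asks about three symptoms. Sedation, itching, urinary retention, constipation, and respiratory depression or use of a reversal agent have no row on either grid, and the grids have no row for other effects. Whatever is not asked at the bedside cannot be fully recovered later.

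Two further features weaken what is collected. First, with no definition and no planned analysis, the summary (worst grade, mean grade, any event, which time points) would be chosen after the data exist. Second, dizziness is not specific to opioids: it is also a named risk of the study drug, of which the active arm receives more.

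At stake is the meaning of the reported result. A finding of no difference in opioid side effects could arise because relevant effects were not asked about, or because the trial is too small to see a modest reduction. A favourable finding could be stated more widely than three symptoms allow.

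**Working it through.** **1. Coverage.** The form has 8 columns from 6 to 48 hours plus 72 hours and 3 weeks, so 10 time points × 3 symptoms = at most 30 scored entries per patient. None is for any other opioid effect. The other routes by which an effect could be recorded are:

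- Immediate and delayed complication fields (Appendix A): yes/no with free text, no grade, placed beside the block details.
- Telephone questions on narcotic side effects at 48 hours, 72 hours and 3 weeks (Procedures Involved): the form's columns for those times list the same three symptoms.
- Untoward events at the surgical visits at about 3 weeks and 1 year (Procedures Involved): no structure given.
- Readmission or emergency visit (Study Endpoints, Appendix A): yes/no.

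These can record an event. They do not give a graded, timed score asked of every patient.

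**2. Block bupivacaine by arm.** Dose = volume × concentration, with 0.25% = 2.5 mg/ml and 0.5% = 5 mg/ml.

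- Control: 10 × 2.5 = 25 mg.
- Active: 10 × 2.5 + 6 × 5 = 55 mg, taking 6 ml as the total. The difference is 30 mg and the ratio 55/25 = 2.2.
- If 6 ml were meant for each of the three sites, which the text does not settle: 25 + 18 × 5 = 115 mg.

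The active arm receives more on either reading. The ratio covers the blocks only: Background says all patients also receive periarticular injections, whose content is not stated.

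**3. Effect of the dizziness overlap.** The documents give no rates, so all of these are assumed: control dizziness p of 10–30%, a 20% relative reduction from opioid sparing, and an added local-anaesthetic risk r in the active arm. The active rate is 1 − (1 − 0.8p)(1 − r).

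| Added risk r | Observed difference, p = 10% | Observed difference, p = 30% |
|---|---|---|
| 0 | 2.0 points | 6.0 points |
| 0.1% | 1.9 | 5.9 |
| 1% | 1.1 | 5.2 |
| 5% | −2.6 | 2.2 |

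Example: p = 10%, r = 1% gives 1 − 0.92 × 0.99 = 8.92%, a difference of 1.1 points. An added 5% would be hard to square with the protocol's word for this risk. The shift always runs against the active arm.

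**4. Power.** The documents give no sample-size figure for side effects. The only one is 47 per arm for opioid consumption, and it reproduces. With difference 9, SD 15, two-sided 0.05 and 80% power, 2 × (15 × (1.960 + 0.842)/9)² = 43.6 per arm. Multiplying by π/3 for the rank test gives 45.7. With the noncentral t distribution and the same efficiency, power is 0.794 at 46 and 0.803 at 47.

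For one yes/no symptom with n = 47 per arm, power = Φ[(d − 1.96·se0)/se1]. Here d is the difference in rates, se0 the pooled and se1 the unpooled standard error.

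- Control 20%, active 16%: (0.04 − 1.96 × 0.0793)/0.0791 = −1.46, power 7%.
- Control 60%, active 48%: (0.12 − 1.96 × 0.1028)/0.1021 = −0.80, power 21%.

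Assumed control rates of 30%, 40% and 50% give about 10%, 12% and 16%.

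**The case against.** A reader might infer that the side-effect hypothesis cannot be answered at all, because one of only three items is confounded with the study drug. The documents do not support that. Nausea and vomiting are not among the listed bupivacaine risks, and they are scored repeatedly in randomized arms by follow-up staff blinded to allocation. That comparison is valid, though narrow. The dizziness risk is called rare, the first grid score is at 6 hours, and any bias works against the active arm, so a finding of fewer side effects would stand.

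A reader might also infer that serious opioid harms would be invisible. That goes too far as well. The complication fields, telephone questions, untoward events and readmission item all offer somewhere to record them. The protocol also provides for a monitoring board and a safety look after 50 subjects. What stands against these routes is that none is shown to ask about specific further opioid effects in a structured way.

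It is also fair to say that the documents do not specify which opioid effects the endpoint must contain, so the exact list is partly a matter of judgement. Neither document mentions antiemetics: that their use could lower nausea and vomiting scores is an assumption.

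**Conclusion.** The concern holds in a limited form. The endpoint is undefined, its structured measurement stops at three symptoms, and no analysis is planned, so the hypothesis of fewer systemic side effects can be only partly tested. The main loss is the symptoms not asked about. The dizziness overlap is minor: under the assumed rates, an added risk of up to 1% takes less than one percentage point off the difference, on one item of three. Low power (about 7–21% for a 20% relative reduction in one symptom, at assumed control rates of 20–60%) means that a null result would say little. The dose contrast of 55 against 25 mg assumes that 6 ml is the total volume and leaves out the periarticular injections. None of this affects the primary outcome.

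**What to change.** **Form.** Add 0–3 rows to both Appendix A grids for sedation, itching, urinary retention, constipation and other effects. Add yes/no entries for respiratory depression or reversal-agent use, and for antiemetic given. The antiemetic entry is a precaution, since the documents do not say whether antiemetics are used.

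**SAP.** Define the endpoint. For each symptom, compare the arms on worst grade, and compare the proportion of patients with any moderate or severe effect. Use a fixed window that nearly all patients complete, chosen before unblinding. It should not end at discharge: length of stay is itself a secondary outcome, so a window ending at discharge would give the arms unequal chances of a high score. Report every symptom separately and give the composite with and without dizziness. Label these comparisons exploratory, because the added symptoms mean more comparisons and power for each is low.

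**Cost.** A form revision and one SAP paragraph, a slightly longer form, and a little more time at contacts already scheduled. No extra visits or patients are needed. The change does not raise power; it broadens what is measured and fixes the analysis in advance.
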